## 2.2. Study Design

This is a prospective, randomized, double-masked (IOP observer and subject), active-controlled, parallel-group, multicenter trial. A total of approximately 150 males and females  $\geq 18$  years of age who were diagnosed with either Open-angle glaucoma (OAG) or Ocular hypertension (OHT) will be randomized to one of three treatment arms in a 1:1:1 allocation:

- [REDACTED]: Travoprost Intraocular Implant, model [REDACTED] (high elution rate) with masked postoperative one drop twice daily (BID) artificial tears in the study eye.
- [REDACTED] Travoprost Intraocular Implant, model [REDACTED] (low elution rate) with masked postoperative one drop BID artificial tears in the study eye.
- Control: Sham surgery with masked postoperative one drop BID topical timolol maleate, ophthalmic solution, 0.5% in the study eye.

Subjects are required to meet all eligibility criteria at the Screening visit. If the subject is using ocular hypotensive medications at this visit, she/he is required to complete the appropriate medication washout period before returning for the Baseline visit. [REDACTED]

Following completion of the baseline visit, eligible subjects are scheduled for the operative examination. At this visit, subjects will be randomized to treatment and per randomized assignment, either implanted with [REDACTED], or have the sham surgical procedure performed.

[figure not shown]
Follow-up visits are scheduled at postoperative Day 1-2, Day 10, Weeks 4, 6, Month 3 and every 3 months thereafter through Month 36. [REDACTED]

Postoperatively, for the duration of the study, subjects in the [REDACTED] arms are instructed to use topical eye drops (artificial tears) twice daily in the study eye, while subjects in the control arm, following sham surgery, are instructed to instill topical timolol 0.5% eye drops, solution twice daily in the study eye. The investigator could administer or prescribe ocular hypotensive medication [REDACTED] at [REDACTED] or later after the operative exam. [REDACTED]  
[REDACTED]

The pre-specified primary efficacy endpoint is IOP at each of the nine time points through 3 months postoperative (8:00 am, 10:00 am, and 4:00 pm at Day 10, Week 6, and Month 3). No formal statistical hypotheses for the efficacy endpoint were specified.

Safety parameters included adverse events and complications, best spectacle-corrected visual acuity, visual field, specular microscopy, cup/disc ratio, slit-lamp examination, fundus examination, and gonioscopy.

### **2.3. Assessment Schedule**

### **2.4. Sample Size Determination**

### 3. Analysis Sets

#### Intent to Treat Analysis Set (ITT)

This analysis set includes all subjects who are randomized. [REDACTED]

[REDACTED]

#### Safety Analysis Set

The safety analysis set will contain all subjects who are randomized and receive at least one dose of study treatment. Subjects will be grouped according to their actual treatment received, [REDACTED]

[REDACTED]

#### Per-Protocol Analysis Set (PP)

The Per-Protocol analysis set is a subset of the ITT analysis set. It includes all the ITT subjects who received the study treatment based on the randomization schedule and do not have major protocol deviations likely to impact the primary efficacy endpoints. [REDACTED]

[REDACTED]

## 4. General Statistical Considerations

Continuous data will be summarized with the number of non-missing values, mean, standard deviation, minimum, median, and maximum. Other selected percentiles, such as the 25th percentile and 75th percentile may be presented for parameters that are not normally distributed or are suspected of exhibiting that tendency. Categorical data will be summarized with the number of non-missing values and the numbers of values equal to each of the possible values. Percentages of subjects with each of the possible values will be calculated from the number of subjects in the relevant cohort of the corresponding analysis set, unless stated otherwise. Some continuous variables may also be grouped into categorical levels and evaluated in frequency tables.

All inferential statistical analyses will be performed with a two-sided confidence level of 95% or a two-sided significance level of 0.05, except when stated otherwise using SAS® software, Version 9.4, or higher.

Data displays produced for this study will include three types: summary tables, data listings, and figures.

Data listings will simply list the data recorded on the case report form (CRF) or derived for each subject. They will be ordered by treatment, subject number, study eye, and time of assessment. Additional levels of ordering may be employed as appropriate. Data listings will not display subject initials.

In general, summary tables will be presented by treatment group:

- [REDACTED] Implant
- [REDACTED] Implant
- Sham/Timolol

### 4.1. Definition of Variables

#### 4.1.1. Baseline

Baseline for analysis purposes is defined as the last assessment prior to treatment start date/time.

#### 4.1.2. Change and Percent Change from Baseline

- Change from baseline is defined as the post baseline value minus the baseline value.
- Percent change from baseline is calculated as follows: Percent change = (Change from baseline / Baseline) \* 100.

#### 4.1.3. Study Days

Study day for analysis purposes is defined as (date of event – surgery date) (+1 if the event occurs on or after surgery start date).

Study Day 1 is the date of surgery. Study Day relative to date of surgery will appear in the listings where applicable.

## 4.2. Analysis Windows

Data at each scheduled follow up visit will be analyzed according to the nominal visit identified on the data record. The order of nominal visits will be consistent with chronological order of the study visit date. All assessments including scheduled and unscheduled will be presented in the data listings.

## 4.3. Adjustment for Covariates

[REDACTED]

[REDACTED]

[REDACTED]

## 4.4. Handling Missing Data

### 4.4.1. Handling of Missing Data/Intercurrent Events for Efficacy Variables

Please see section 6.1.3 for handling missing IOP data/intercurrent events for the primary analysis.

### 4.4.2. Imputation of Incomplete Medication/AE Dates

For analyses of adverse events (AEs) and concomitant medication usage, a complete date must be established in order to correctly identify the AE or medication as occurring during treatment or not. For purposes of imputing missing components of partially reported start and stop dates for AEs and for medication use, the algorithms listed below will be followed. Start and stop dates of AEs or concomitant medication will be displayed as reported in the subject data listings (i.e., no imputed values will be displayed in data listings).

[REDACTED]

[REDACTED]

[REDACTED]

[REDACTED]

[REDACTED]

[REDACTED]

[REDACTED]

#### 4.5. Multiple Study Centers

## 5. Demographic and Baseline Characteristic Analyses

### 5.1. Subject Disposition

Reasons for screen-failure (including baseline-failure, i.e., subjects enrolled but not randomized) will be tabulated.

Exit status will be classified as completed or discontinued (including reason for discontinuation) for each randomized subject. The reasons for premature discontinuation are:

Exit status will be summarized as number and percent by treatment group and overall for the ITT analysis set.

The number of subjects who were randomized and the number of subjects within each analysis set (ITT, Safety, and PP) will be summarized by treatment group.

Subject disposition data will be provided in a listing. A separate listing describing each subject's inclusion or exclusion status for each of the analysis sets will also be provided.

### 5.2. Protocol Deviations

Protocol deviations will be captured in the eCRF and reviewed by medical monitor during the study. Classification between major or minor deviations will be decided by the study team prior to database lock. Subjects with major protocol deviations will be excluded from PP analysis set.

All protocol deviations will be listed and summarized by type and treatment group for the ITT analysis set.

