**9.5.4.3. Per Protocol Population (PP)**

The Per Protocol Population is a subset of ITT. It includes all the ITT subjects who received the treatment and medication drops based on the randomization schedule and do not have the major protocol deviations. The major protocol deviations will be determined with the study Medical Monitor in a mask fashion prior to the database lock for the final analyses for the 12-week data. The PP population will be used in the sensitivity analysis for the mean IOP comparisons.

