## 1. Introduction

This Phase 2 study evaluates the safety and efficacy of two intraocular implants that elute travoprost at different rates in subjects with open-angle glaucoma (OAG) or ocular hypertension (OHT). The study duration is 36 months postoperative. One database lock will occur after all subjects have either completed the Month 36 visit or discontinued prematurely.

An analysis will be conducted after all subjects either completed the Month 3 visit or have discontinued prematurely prior to Month 3. At that time, the randomization code will be unmasked to the project team after all the data queries related to the efficacy and safety outcomes are resolved and corresponding data revisions are completed in the database.

This statistical analysis plan provides details of the planned analyses to be performed at the time of the Month 36 database lock. Shells of tables, listings and figures are presented in a separate document.

[figure not shown]
This document is based on Protocol Amendment 2 (16 September 2016). The statistical definitions and analytical methods described in this SAP supersede that in the protocol. Any revisions to the primary endpoint analyses and significant revisions to the secondary endpoint analyses will be made prior to the database lock. Reasons for such revisions will be described in the final Clinical Study Report (CSR).

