### 6.1.6. Sensitivity Analyses

To evaluate the robustness of the primary analysis results, the following sensitivity analyses of the primary efficacy endpoints will be performed, including different imputation methods for missing data:

#### 1. Sensitivity Analysis 1

Same as the primary analysis, a t-test will be performed for the Per-Protocol analysis set on observed case (OC).

#### 2. Sensitivity Analysis 2

#### 3. Sensitivity Analysis 3

A t-test using the last observation carried forward (LOCF) method described in Section 6.1.3 will be performed for the ITT analysis set.

#### 4. Sensitivity Analysis 4

[figure not shown]

[figure not shown]
#### 5. Sensitivity Analysis 5

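### SAP 5.2 lets per-protocol membership be settled up to the Month 36 lock with no masking rule, although the code is released at Month 3 and the protocol requires a masked decision before the 12-week lock

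*SAP*

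**What the plan says.** **Protocol.** Section 9.5.4.3 says that major deviations are "determined with the study Medical Monitor in a mask fashion prior to the database lock for the final analyses for the 12-week data". Section 9.3 then releases the code to the project team once the 12-week data have been queried and corrected.

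**SAP.**
- Section 1 describes a single lock: "One database lock will occur after all subjects have either completed the Month 36 visit or discontinued prematurely".
- Section 1 also provides for an analysis once all subjects have reached Month 3 or left the study. Of that point it says "At that time, the randomization code will be unmasked to the project team", once queries on the efficacy and safety outcomes are closed. No lock is named there.
- Section 1 adds: "The statistical definitions and analytical methods described in this SAP supersede that in the protocol".
- Section 5.2 has the medical monitor review deviations during the study, but on the major/minor decision it says: "Classification between major or minor deviations will be decided by the study team prior to database lock". Masking is not mentioned.
- Section 3 limits the PP set to correctly treated ITT subjects who "do not have major protocol deviations likely to impact the primary efficacy endpoints". The text that follows is redacted.
- Section 5.2 is broader: "Subjects with major protocol deviations will be excluded from PP analysis set".
- Section 6.1.6 uses the PP set for Sensitivity Analysis 1, an observed-case t-test of the primary endpoints. Those endpoints are IOP at three clock times on Day 10, Week 6 and Month 3.

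**The concern.** A per-protocol set protects against selective exclusion only if membership is decided without knowledge of treatment. The protocol provides for that with masking, Medical Monitor involvement and a deadline tied to the 12-week data. The visible SAP classification rule carries over none of the three. Because the SAP states that its definitions prevail, a reader cannot assume that the protocol's rule still governs.

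There is also a mismatch inside the SAP. Under section 3, only deviations that matter for the primary endpoints remove a subject. Under 5.2, any major deviation does. A major deviation in year 2 or 3 cannot affect IOP measured by Month 3, yet 5.2 would still remove that subject from Sensitivity Analysis 1. This point does not depend on who is unmasked.

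What is at stake is whether the PP t-test can serve as evidence of robustness, which is its purpose in SAP 6.1.6. The planned listing of each subject's set status (SAP 5.1) will show who was excluded, but not whether the decision came before the codes were known.

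**Working it through.** **1. The two rules side by side**

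| | Protocol 9.5.4.3 | SAP 5.2 with SAP 1 |
|---|---|---|
| Who decides | With the Medical Monitor | Study team; the monitor reviews during the study |
| Masked | Yes | Not stated |
| Deadline | Lock for the 12-week data | Database lock; the only one defined follows Month 36 |
| Code release to project team | After 12-week data cleaning (9.3) | At the Month 3 analysis, after data cleaning |

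Under the protocol, masked classification comes before the 12-week lock. Under the SAP the order can be code release first and classification later.

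**2. How long classification can stay open**

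Protocol 4.1 puts Week 12 (Month 3 in the SAP) at day 91 ± 7 and Month 36 at day 1095 ± 60. The nominal gap per subject is 1095 − 91 = 1004 days. With the windows it is 1004 ± 67, or 937 to 1071 days. The calendar dates of unmasking and lock are not given, so this is only an approximation.

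**3. Possible effect on the PP comparison (illustrative)**

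Inputs:
- 50 per arm, from about 150 subjects at 1:1:1 (both documents).
- SD of 3.0, 3.5 or 4.0 mmHg. This is an assumption; no SD is visible in the documents.
- Two to five exclusions in one arm. This is also an assumption.
- One timepoint, normally distributed IOP, no covariate adjustment.

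CI half-width = t(0.975, 98) × SD × √(2/50), which gives 1.191, 1.389 and 1.588 mmHg.

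Removing k subjects whose mean lies d above the arm mean shifts that mean by −k·d/(50 − k). Expected shifts for the first four rows come from 50,000 simulated normal arms of 50:

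| Exclusions from one arm | SD 3.0 | SD 3.5 | SD 4.0 | Share of half-width |
|---|---|---|---|---|
| Two highest | −0.256 | −0.299 | −0.342 | 22% |
| Three highest | −0.366 | −0.427 | −0.488 | 31% |
| Five highest (worst case) | −0.568 | −0.663 | −0.757 | 48% |
| Five at random from the upper 25 | −0.261 | −0.306 | −0.349 | 22% |
| Five at random from all 50 | 0 expected | 0 expected | 0 expected | 0% |

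In the last row, chance alone gives a shift with standard deviation SD × √(5/(50 × 45)) = 0.141, 0.165 and 0.189 mmHg.

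**The case against.** The strongest objection is the redaction. In the protocol the masking sentence directly follows the PP definition, and the corresponding place in SAP section 3 is blacked out. A freeze rule may be there. That limits the point to the visible text, but 5.2 would still need to refer to such a rule.

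Second, the supersession clause covers definitions and methods. Who reviews deviations, and whether they are masked, is arguably trial conduct, so the protocol's rule may survive. The SAP deadline is also an outer limit: a masked list fixed at Month 3 would satisfy both documents. This is fair, but the visible SAP neither requires nor cites such a list.

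Third, the SAP is written for the Month 36 lock, and deviations after Month 3 cannot be classified earlier. That explains a late deadline for reporting them. It does not explain letting them alter the PP set for an endpoint that ends at Month 3.

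Fourth, bias needs several links. The study team must overlap the unmasked project team (neither is defined), no earlier list may exist, and knowledge of codes must influence the decisions. None of this is established, only left possible.

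Fifth, the effect is small. PP is one of five sensitivity analyses, the primary analysis is ITT on observed cases (SAP 6.1.5), and SAP 2.2 says no formal efficacy hypotheses were specified. The worst case models one of nine timepoints, and subjects highest at one need not be highest at the others. All of this stands and keeps the point below the level of a threat to the primary result.

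Finally, the qualifier in section 3 could be read as explaining what major means. If so, 5.2 should say so, because as worded it has no such limit.

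**Conclusion.** The concern holds on the visible text. SAP 5.2 contains no masked freeze before Month 3, its deadline falls roughly 1004 days after the Month 3 visit by nominal visit days, and it excludes more broadly than SAP section 3.

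The masking part is conditional on overlap between the study and project teams and on no redacted or separate document already fixing the list. The mismatch between section 3 and 5.2 does not depend on who is unmasked, though a redacted definition of major could resolve it.

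The primary analysis is untouched. Even the assumed worst case moves the PP difference by less than half the CI half-width, so the damage would be to the credibility of Sensitivity Analysis 1 more than to its direction. The change should be made; confidence is medium because of the redactions.

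**What to change.** Reword SAP 5.2 to say that, for the Day 10 to Month 3 endpoint, major deviations and PP membership are determined masked with the Medical Monitor, then signed and frozen before the Month 3 code release. State that later deviations are classified for reporting and do not reopen that list. Carry the section 3 limit on relevance to the primary endpoints into 5.2 so that the two agree.

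- If a masked list already exists, cite its date and state that it is frozen.
- If codes have been released and no list exists, use reviewers without access to them and disclose the timing in the clinical study report.
- If the redacted part of section 3 already contains the rule, cross-reference it from 5.2.

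The cost is SAP wording only. It restores the protocol's own rule and needs no new data or analysis.

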### 5.3. Demographic and Baseline Characteristics

Demographic and baseline subject characteristics will be summarized for the ITT analysis set. Demographics will include age, sex with child-bearing potential for females, race, and ethnicity.

The baseline clinical characteristics include the following variables:

- Type of disease (OAG or OHT)
- Disease Duration from Time of Diagnosis (years)
- Baseline Study Eye IOP
- Baseline best spectacle corrected visual acuity in study eye - LogMAR
- Iris Color for study eye

- Visual Field Mean Deviation (dB) for study eye
- Visual Field Pattern Standard Deviation (dB) for study eye
- Vertical Cup-to-Disc Ratio for study eye
- Corneal Thickness (μm) for study eye

A listing of demographic and baseline information will be provided.

#### **5.4. Medical and Surgical History**

Medical and surgical history including ocular and non-ocular (systemic) medical/surgical history will be collected in the eCRF. Ocular and non-ocular medical/surgical history will be presented in listings.

#### **5.5. Prior and Concomitant Medications/Procedures**

##### Prior and Concomitant Medications

Prior medication is defined as any medication taken prior to the date of the surgery. Concomitant medication is defined as any medication taken on or after the surgery date. If any medication is taken before the surgery date and continues after the surgery date, it will be considered as both a prior and concomitant medication.

Prior/concomitant medications will be coded to therapeutic class and preferred term using the World Health Organization Drug Dictionary [REDACTED]

The number and percentage of subjects who had taken prior/concomitant medications will be summarized by therapeutic class and preferred term, and by treatment group. Subjects taking the same medication multiple times will only be counted once for that therapeutic class and preferred term. A subject level listing will also be presented.

##### Concurrent Ocular Procedures

Concurrent ocular procedure is defined as any ocular procedures performed for the study eye after the surgery date. Concurrent ocular procedures will be provided in a listing.

##### Non-study IOP Lowering Medications

A non-study IOP-lowering medication is defined as a non-study IOP-lowering medication taken for the study eye. [REDACTED]

The number and percentage of subjects [REDACTED] will be summarized by type of disease and treatment group.

A listing of the prior and concomitant non-study IOP-lowering medications for study eye will be provided.

## 6. Efficacy Analyses

### 6.1. Primary Efficacy Endpoints Analysis

#### 6.1.1. Definition of Endpoints

The primary efficacy measure in this study is IOP. Diurnal IOP (measured at 8AM, 10AM, and 4PM) is evaluated at Baseline, Day 10, Week 6, and Month 3. Standard IOP (measured at 8AM) is evaluated at Week 4 and Months 6, 9, 12, 15, 18, 21, 24, 27, 30, 33, and 36. [REDACTED]

The primary efficacy endpoint is the diurnal IOP in the study eye at 8AM, 10AM, and 4PM at each of Day 10, Week 6, and Month 3 visits (9 timepoints).

#### 6.1.2. Statistical Hypotheses

#### 6.1.3. Handing of Missing Data/Intercurrent Events for Efficacy Variables

The approaches listed below will be used for handling missing data/intercurrent events:

- **Observed Case (OC):** Missing data are not imputed. Only subjects with available data at the given time point are considered. OC will be the primary approach in the analysis of continuous efficacy variables.
- **Last Observation Carried Forward (LOCF):** The LOCF analyses will use the last observed non-missing, time consistent, evaluation for efficacy measures assessed to impute missing data at later visits. Baseline efficacy evaluations will not be carried forward. LOCF will be the secondary approach for sensitivity analysis of primary and secondary efficacy endpoints.

[REDACTED]

A high-contrast, black and white image showing a complex, abstract pattern of geometric shapes. The pattern consists of several large, solid black rectangles of varying widths and heights, arranged in a staggered, overlapping fashion. The background is white, and the edges of the rectangles are sharp, creating a digital or graphic design aesthetic. The overall composition is abstract and lacks any recognizable objects or text.

3

[REDACTED]

[figure not shown]

- **Non-Responder Imputation (NRI):** Subjects who have missing data or intercurrent events at the timepoint of interest are treated as though they did not respond to the treatment. NRI will be applied to the responder analyses.

#### 6.1.4. Multiplicity Adjustment

A horizontal redaction bar is located just below the section header, spanning approximately 70% of the page width.

#### 6.1.5. Primary Analysis

A large rectangular area of the page has been completely redacted with black ink, obscuring several lines of text. The redaction is approximately 15 lines high and 10 lines wide.

The primary analysis will be performed for the ITT analysis set based on the observed case (OC), i.e., without missing data imputation.

